7.1.3. Relationship of Adverse Events to Study Drug

Related AEs are those for which the investigator selected “Related” on the AE CRF to the question of “Related to Study Treatment.” Relatedness will always default to the investigator’s choice, not that of the medical monitor. Events for which the investigator did not record relationship to study drug will be considered related to study drug for summary purposes. However, by-subject data listings will show the relationship as missing.

7.1.4. Serious Adverse Events

Serious adverse events (SAEs) will be identified and captured as SAEs if the AEs met the definitions of SAEs that are specified in the study protocol. SAEs captured and stored in the clinical database will be reconciled with the SAE database from then Gilead Global Safety Department before data finalization.

7.1.5. Treatment-Emergent Adverse Events

7.1.5.1. Definition of Treatment-Emergent Adverse Events

Treatment-emergent adverse events (TEAEs) are defined as 1 or both of the following:

- Any AEs with an onset date on or after the study drug start date and no later than 30 days after permanent discontinuation of study drug
- Any AEs leading to permanent discontinuation of study drug.

7.1.5.2. Incomplete Dates

If the onset date of the AE is incomplete and the AE stop date is not prior to the first dosing date of study drug, then the month and year (or year alone if month is not recorded) of onset determine whether an AE is treatment emergent. The event is considered treatment emergent if both of the following 2 criteria are met:

- The AE onset is the same as or after the month and year (or year) of the first dosing date of study drug, and
- The AE onset date is the same as or before the month and year (or year) of the date corresponding to 30 days after the date of the last dose of study drug.

An AE with completely missing onset and stop dates, or with the onset date missing and a stop date later than the first dosing date of study drug, will be considered to be treatment emergent. In addition, an AE with the onset date missing and incomplete stop date with the same or later month and year (or year alone if month is not recorded) as the first dosing date of study drug will be considered treatment emergent.

In case when the AE onset date is incomplete and needs to be imputed, the following algorithm will be followed:

- If the day is missing but the month and year are available, then the imputed day will be the first day of the month or the first dosing date if they have the same month and year, whichever is later.
- If the day and month are missing but year is available, then the imputed day and month will be 01 Jan or the first dosing date if they have the same year, whichever is later.

7.1.6. Summaries of Adverse Events and Deaths

TEAEs will be summarized by treatment arms based on the Safety Analysis Set.

7.1.6.1. Summaries of Adverse Events Incidence by Severity

The number and percentage of subjects who experienced at least 1 TEAE will be provided and summarized by SOC and PT.

The number and percentage of subjects who experienced at least 1 TEAE will be provided and summarized by PT and severity in descending order of total frequency:

- Treatment-Emergent Adverse Events by PT and Severity

For the AE categories described below, summaries will be provided by PT in descending order of total frequency:

- All Treatment-Emergent Adverse Events
- Grade 4 or Higher Treatment-Emergent Adverse Events
- Grade 3 or Higher Treatment-Emergent Adverse Events
- Treatment-Emergent Idelalisib related Adverse Events
- Treatment-Emergent Serious Adverse Events
- Treatment-Emergent Idelalisib related Serious Adverse Events
- Treatment-Emergent Adverse Events leading to discontinuation of Idelalisib
- Treatment-Emergent Adverse Events leading to temporary interruption of Idelalisib
- Treatment-Emergent Adverse Events leading to study discontinuation
- Treatment-Emergent Adverse Events leading to Death

A brief, high-level summary of AEs described above will be provided by treatment arms and by the number and percentage of subjects who experienced the above AEs.

For summaries of TEAEs by PT, multiple events will be counted only once per subject in each summary. Adverse events will be summarized and listed by PT in descending order of total frequency. For summaries by severity, the most severe severity will be used for those AEs that occurred more than once in a given subject during the study.

In addition, by-subject data listings will be provided by treatment arms and subject ID number in ascending order for the following:

- All AEs, indicating whether the event is treatment emergent
- All SAEs
- All Deaths
- All Adverse Events leading to Death
- All Adverse Events with Grade 3 or Higher
- All Adverse Events with Grade 4 or Higher

- All Adverse Events leading to discontinuation of Idelalisib
- All Adverse Events leading to temporary interruption of Idelalisib
- All Adverse Events leading to study discontinuation

A flag will be included in the listings to indicate whether the event is treatment emergent.

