8.1.3. Secondary Endpoints

The secondary endpoints are as follows:

- DOR, defined as the interval from the first documentation of CR or PR to the earlier of the first documentation of disease progression by IRC or death from any cause
- ORR by Week 24, defined as the proportion of subjects who achieve a PR or CR by Week 24
- Overall safety profile of idelalisib, including the incidence of AEs and clinically significant laboratory abnormalities, severity, timing, and relationship to idelalisib of any AEs; SAEs; or AEs leading to interruption, reduction, or discontinuation of idelalisib

- Time to onset of AEs, defined as the interval from the start of idelalisib treatment to the first documentation of start of AEI
- PFS, defined as the interval from randomization to the earlier of the first documentation of disease progression by IRC or death from any cause
- OS, defined as the interval from randomization to death from any cause
- Idelalisib trough (predose) and peak (1.5-hour samples) plasma concentrations assessed by validated bioanalytical method

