8.6.2. Adverse Events

All AEs will be listed. The focus of AE summarization will be on treatment-emergent AEs. A treatment-emergent AE is defined as any AE with onset date on or after the date of first dose of study drug up to 30 days after permanent study drug discontinuation or any AEs leading to premature study drug discontinuation.

AEs will be classified using Medical Dictionary for Regulatory Activities with descriptions by system organ class (SOC), high-level group term, high-level term, preferred term (PT), and lower-level term. The severity of AEs will be graded by the investigator according to the CTCAE, Version 5.0, whenever possible. If a CTCAE criterion does not exist for a specific type of AE, the grade corresponding to the appropriate adjective will be used by the investigator to describe the intensity of the AE: Grade 1 (mild), Grade 2 (moderate), Grade 3 (severe), Grade 4 (life threatening), or Grade 5 (fatal). The relationship of the AE to the study drug will be categorized as related or unrelated.

For the primary safety endpoint, the number and percentage of subjects who experienced at least one Grade ≥ 4 TEAE will be listed and summarized by SOC and PT, and by treatment arm in the Safety Analysis Set. The severity, timing, relationship to study drug, drug interruptions, reductions, and discontinuations for Grade ≥ 4 TEAEs will be summarized.

Summaries (number and percentage of subjects) of TEAEs by SOC and PT will be provided. A subject who reports multiple TEAEs within the same PT (or SOC) is counted only once for that PT (or SOC) using the worst severity grade. AE descriptions will be presented by decreasing frequency for a given SOC and PT.

Separate summaries will be prepared for the following types of TEAEs:

- Idelalisib-related AEs
- AEs that are Grade ≥ 4 in severity

- AEs that are Grade ≥ 3 in severity
- AEs leading to study drug interruption, reduction, or discontinuation
- SAEs

Additional analysis on AEs will be performed. The AEs include: Grade ≥ 3 diarrhea/colitis, rash, febrile neutropenia, infection, and any grade of the following: pneumonitis, bowel perforation, progressive multifocal leukoencephalopathy (PML), PJP, CMV infection, and organizing pneumonia. The frequency, severity, timing, and drug interruptions for AEs will be summarized by treatment arm using descriptive statistics. Time to first onset of AEs and time to resolution will be summarized using the Kaplan-Meier method.

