1.2.2. Secondary Endpoints

- DOR, defined as the interval from the first documentation of CR or PR to the earlier of the first documentation of disease progression by independent review committee (IRC or death from any cause
- ORR by Week 24, defined as the proportion of subjects who achieve a PR or CR by Week 24
- Overall safety profile of idelalisib, including the incidence of AEs and clinically significant laboratory abnormalities, severity, timing, and relationship to idelalisib of any AEs; SAEs; or AEs leading to interruption, reduction, or discontinuation of idelalisib Time to onset of AEs of interest (AEIs) defined as the interval from the start of idelalisib treatment to the first documentation of start of AEI
- PFS, defined as the interval from randomization to the earlier of the first documentation of disease progression by IRC or death from any cause
- OS, defined as the interval from randomization to death from any cause
- Idelalisib trough (predose) and peak (1.5-hour samples) plasma concentrations assessed by validated bioanalytical method

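### The SAP plans no summary or listing of TEAEs leading to dose reduction, although its own secondary endpoint and Protocol 8.6.2 name them, and SAP 7.6 does not declare the omission

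*SAP*

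**What the plan says.** **Endpoint.** The overall-safety secondary endpoint covers three dose actions. SAP 1.2.2 includes "AEs leading to interruption, reduction, or discontinuation of idelalisib", and Protocol 8.1.3 has the same wording: "SAEs; or AEs leading to interruption, reduction, or discontinuation of idelalisib".

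**Protocol analysis.** Protocol 8.6.2 calls for a separate TEAE summary of "AEs leading to study drug interruption, reduction, or discontinuation". Within the primary safety endpoint it also asks for a summary of dose actions: "The severity, timing, relationship to study drug, drug interruptions, reductions, and discontinuations for Grade" ≥4 TEAEs. Protocol 8.6.1 adds how many dose interruptions and reductions there were, and when.

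**SAP analysis.** SAP 7.1.6.1 lists "Treatment-Emergent Adverse Events leading to discontinuation of Idelalisib" and "Treatment-Emergent Adverse Events leading to temporary interruption of Idelalisib" among its by-preferred-term summaries, with matching listings such as "All Adverse Events leading to temporary interruption of Idelalisib". Neither list has an entry for reduction. SAP 4.2 summarizes total duration of exposure, ignoring temporary interruptions, and its dosing listing gives the reason for interruption only.

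**Declared changes.** SAP 7.6 records one departure from the protocol's safety analyses, the dropped time to onset of adverse events of interest. SAP Section 1 gives the SAP's specified methods precedence over the protocol where the two differ, and says changes after finalization go into the CSR.

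**The concern.** The SAP repeats an endpoint with three named components and then specifies outputs for two of them. If the programming follows SAP 7.1.6.1 and 4.2 as written, the reduction component is not reported by arm anywhere.

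The study is titled a dose optimization study. Protocol 1.3 sets the goal of learning whether the alternative schedule can match the approved regimen's efficacy with less toxicity. Arms A and C start at the same 150 mg twice-daily dose and both have a 100 mg twice-daily reduced level (Table 5-1). How many subjects moved to that level, and when, bears directly on comparing the two schedules. A reader of the CSR would expect to find it, because both documents promise it.

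**Working it through.** No sample size, power or alpha is involved, and the plan gives no figure to reproduce. The check compares the texts and counts entries.

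**1. What was promised against what is planned**

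| Item | Promised in | Planned in the SAP |
|---|---|---|
| TEAEs leading to interruption | SAP 1.2.2; Protocol 8.1.3, 8.6.2 | Yes, 7.1.6.1 summary and listing |
| TEAEs leading to drug discontinuation | SAP 1.2.2; Protocol 8.1.3, 8.6.2 | Yes, 7.1.6.1 summary and listing |
| TEAEs leading to reduction | SAP 1.2.2; Protocol 8.1.3, 8.6.2 | No |
| Reductions for Grade ≥4 TEAEs | Protocol 8.6.2 | No |
| Number and timing of reductions | Protocol 8.6.1 | No, absent from 4.2 |

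**2. Count of outputs in SAP 7.1.6.1**

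- By-preferred-term summaries, 10: all TEAEs; Grade 4 or higher; Grade 3 or higher; related; serious; related serious; leading to drug discontinuation; to interruption; to study discontinuation; to death. For reduction: 0 of 10.
- Listings, 9: all AEs; SAEs; deaths; AEs leading to death; Grade 3 or higher; Grade 4 or higher; leading to drug discontinuation; to interruption; to study discontinuation. For reduction: 0 of 9.
- The high-level summary is built from the categories above it, so it has the same gap.

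**3. Role of the reduced dose in Protocol Table 5-2**

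- Rules that withhold or interrupt drug, 9: Grade 1 pneumonitis; CMV; Grade ≥3 rash; PML; Grade 3 ALT/AST; Grade 3 bilirubin; Grade ≥3 or persistent Grade 2 diarrhea/colitis; Grade 4 neutropenia; Grade 4 thrombocytopenia.
- Of these, rules that allow restart at the reduced dose: 9 − 2 (CMV and PML) = 7. No other restart level is named.
- Rules that discontinue drug, 8: Grade ≥2 pneumonitis; PJP; organizing pneumonia; SJS/TEN; bowel perforation; Grade 4 ALT/AST; Grade 4 bilirubin; Grade 4 diarrhea/colitis.
- Rules that reduce the dose without a hold first: 0.

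**4. What the planned outputs can and cannot show**

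Since each of the 7 rules starts with a hold, the triggering event may appear in the interruption summary. That summary counts the hold, however, and a subject who resumes at 150 mg and one who resumes at 100 mg contribute to it identically. The Grade ≥3 and Grade ≥4 summaries record severity, not the dose afterwards. SAP 4.2 reports duration, not dose level. No planned summary therefore separates the two kinds of restart by arm.

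**The case against.** The strongest reply is that little is lost. Table 5-2 requires a hold or discontinuation and only permits the reduced dose at restart. The events that lead to a reduction should therefore largely be in the interruption summary already, and severe ones also in the Grade ≥3 or Grade ≥4 summaries. Protocol 1.4 describes the hoped-for benefit of Arm C as less toxicity and fewer interruptions, and interruptions are tabulated. The study is descriptive, has no formal testing (SAP 3.5), and was terminated early (SAP Section 1).

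Much of this stands, and it rules out several stronger readings that a reader might infer:

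- *Reduction is the main dose response to toxicity.* The documents do not say so. Protocol 1.3 lists interruption, reduction, re-escalation and discontinuation without ranking them, and in Table 5-2 reduction is an optional step after a hold.
- *An arm with many reductions would look as tolerable as one held at full dose.* This ignores the interruption and severity summaries. Protocol 5.3.1 also allows re-escalation after at least 4 weeks at the reduced dose, so a reduction does not establish that a subject could not hold the assigned dose.
- *The precedence clause cancels the protocol's reduction analysis.* That clause covers methods the SAP specifies. The SAP specifies nothing on reductions, so the text shows an undeclared gap and no clear override.
- *A zero count in Arm B would be structural.* The synopsis says reductions are not available in Arm B, but Protocol 3.3 allows escalation to 150 mg twice daily. Under SAP 3.2 escalated subjects stay grouped in Arm B, because their treatment did not differ from the randomized one for the whole duration. The documents do not state reduction rules for them.

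The reply does not supply the missing output. How far the interruption summary covers these events depends on how the eCRF codes action taken, which the documents do not give. If only one action can be recorded per event, those coded as reduced would drop out of it. The all-AE listing might show action taken, but SAP 7.1.6.1 does not say so, and a listing is not a by-arm summary.

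**Conclusion.** The gap is real and worth correcting. A component named in the SAP's own secondary endpoint has no planned summary or listing, the protocol's exposure summary of reductions is missing as well, and SAP 7.6 is silent on both.

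Its size is limited. It concerns reporting of a descriptive secondary safety endpoint, plus the protocol's supporting detail on reductions for Grade ≥4 TEAEs. It does not touch ORR, the headline Grade ≥4 TEAE incidence, the sample size or any error rate. How many subjects are affected cannot be estimated, since the documents give no reduction rates. The conclusion that stepping down cannot be separated from resuming at full dose assumes the interruption summary is produced as SAP 7.1.6.1 describes it, with no breakdown by restart dose.

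**What to change.** - In SAP 7.1.6.1, add TEAEs leading to idelalisib dose reduction, by arm, to the preferred-term summaries, the high-level summary and the listings. Include reductions for Grade ≥4 TEAEs, as Protocol 8.6.2 provides.
- In SAP 4.2, add the number and timing of dose reductions by arm, as Protocol 8.6.1 provides.
- Because the SAP is signed, document the additions in the CSR, the route SAP Section 1 sets out. If the sponsor chooses not to produce them, declare and justify both omissions there.
- Do not footnote an Arm B zero as structural. Report what was recorded, and say how escalated subjects are counted.

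The cost is roughly one summary table and one listing from the action-taken data, a row in the high-level summary, and an extension of the exposure table. This assumes action taken and dose level were recorded, as the planned interruption and discontinuation outputs suggest. No new data collection would then be needed.

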7.1.6.2. Summary of Deaths

A summary (number and percentage of subjects) of deaths will be provided by treatment arms. The summary will include the following categories:

- All deaths
- Deaths within 30 days of the last dosing of study drug
- Deaths beyond 30 days of the last dosing of study drug.

Every attempt will be made to ensure that complete death dates are recorded. In those rare instances where complete death dates are not recorded, the following algorithm will be used:

- If day is missing but the month and year are available, then the imputed date will be the 1st day of the month or the last known alive date + 1, whichever is later.

A by-subject listing of all deaths occurred during this study will be provided by treatment arms and subject ID number in ascending order.

7.2. Laboratory Evaluations

Laboratory data collected during the study will be analyzed and summarized using both quantitative and qualitative methods. Summaries of laboratory data will be provided for the Safety Analysis Set and will include data collected up to the last dose of study drug plus 30 days. The analysis will be based on values reported in conventional units. When values are below the LOQ, they will be listed as such, and the closest imputed value will be used for the purpose of calculating summary statistics as specified in Section 3.5.

A by-subject listing for all lab test results will be provided by treatment arms, subject ID number and time point in chronological order for hematology and serum chemistry, separately. Values falling outside of the relevant reference range and/or having a severity Grade of 1 or higher on the CTCAE severity grade will be flagged in the data listings, as appropriate.

No formal statistical testing is planned.

7.2.1. Graded Laboratory Values

CTCAE Version 5.0 will be used to assign toxicity Grades (0 to 4) to laboratory results for analysis. Grade 0 includes all values that do not meet the criteria for an abnormality of at least Grade 1. For laboratory tests with criteria for both increased and decreased levels, analyses for each direction (ie, increased, decreased) will be presented separately.

Local labs will be graded based on central lab normal ranges with in-house macro. Baseline grade will be based on central laboratory results, unless only local labs are collected prior to the first dosing of study drug. For post-baseline grade, the worst toxicity grade considering both central and local lab results will be used for the summary of lab toxicities. All central and local laboratory values will be listed for All Enrolled Subjects.

7.2.1.1. Treatment-Emergent Laboratory Abnormalities

Treatment-emergent laboratory abnormalities are defined as values that increase at least 1 toxicity grade from baseline at any postbaseline time point, up to and including the date of last dose of study drug plus 30 days for subjects who permanently discontinued study drug, or the last available date in the database snapshot for subjects who were still on treatment at the time of an analysis. A baseline laboratory value will be defined as the last measurement obtained on or prior to the date/time of first dose of study drug. If the relevant baseline laboratory value is missing, any abnormality of at least Grade 1 observed within the time frame specified above will be considered treatment emergent.

7.2.1.2. Summaries of Laboratory Abnormalities

The following summaries (number and percentage of subjects) for treatment-emergent laboratory abnormalities will be provided by lab test and treatment arm; subjects will be categorized according to the most severe postbaseline abnormality grade for a given lab test:

- TE laboratory abnormalities

In the summary of laboratory abnormalities, the denominator is the number of subjects with nonmissing postbaseline values up to 30 days after last dosing date.

7.3. Body Weight and Vital Signs

A by-subject listing of body weight and vital signs will be provided for All Enrolled Subjects by treatment arms subject ID number and visit in chronological order.

7.4. Prior and Concomitant Medications

Medications collected at screening and during the study will be coded using the current version of the World Health Organization Drug dictionary. Listings will be provided for All Enrolled Analysis Set.

7.4.1. Prior Medications

Prior medications are defined as any medications begun before a subject took the first study drug.

For the purposes of analysis, any medication with a start date prior to the first dosing date of study drug will be considered as prior medication regardless of when the stop date is. If a partial start date is entered the medication will be considered prior unless the month and year (if day is missing) or year (if day and month are missing) of the start date are after the first dosing date. Medications with a completely missing start date will be considered as prior medication, unless otherwise specified.

All prior medications (other than per-protocol study drugs) will be provided in a by-subject listing sorted by treatment arms, subject ID number and administration date in chronological order based on All Enrolled Analysis Set.

7.4.2. Concomitant Medications

For the purposes of analysis, concomitant medications are defined as any medications

- started prior to or on the first dosing date of study drug and continued to be taken after the first dosing date, or
- started after the first dosing date but prior to or on the last dosing date of study drug.

Medications started and stopped on the same day as the first dosing date or the last dosing date of study drug will also be considered concomitant. Medications with a stop date that is prior to the date of first dosing date of study drug or a start date that is after the last dosing date of study drug will not be considered as concomitant medication.

If a partial stop date is entered, any medication with the month and year (if day is missing) or year (if day and month are missing) prior to the date of first study drug administration will not be considered as concomitant medication. If a partial start date is entered, any medication with the month and year (if day is missing) or year (if day and month are missing) after the study drug stop date will not be considered as concomitant medication. Medications with completely missing start and stop dates will be considered as the concomitant medication, unless otherwise specified.

All concomitant medications (other than per-protocol study drugs) will be provided in a by-subject listing sorted by treatment arms, subject ID number and administration date in chronological order based on All Enrolled Analysis Set.

